This work will utilize existing investigative collaborations as part of my NIH K23 award application that is under review. [name] has conducted more than 1,000 invasive exercise hemodynamic studies for both clinical and research purposes, and has published extensively on invasive exercise hemodynamics in patients with heart failure and PAH.¹⁴⁻¹⁷ Here, I will apply these same techniques to again characterize convective O_2 transport as in prior studies of HF, but in order to now evaluate peripheral diffusive O_2 transfer, I will work together with [name], who has extensive investigative experience in peripheral O_2 transfer.¹⁸⁻²⁰ To further characterize mitochondria in muscle, I will also work closely with [name], who is a world expert in mitochondrial biology and quantifying oxidative capacity.^{21,22,22,23} Under the mentorship of this multidisciplinary team, I will be able to comprehensively study O_2 transfer from the lungs to skeletal muscle mitochondria in PAH-ILD and better understand exercise intolerance in these patients and the effects of inhaled treprostinil on exertion.

G. Study design:

Hypothesis #1 Patients with ILD-PAH will have impaired cardiac output reserve and leg blood flow during exercise, and inhaled treprostinil will acutely increase exertional cardiac output with preserved skeletal muscle O_2 uptake efficiency.

Research Design for Hypothesis #1: This will be a prospective study 24 patients with PAH-ILD undergoing cardiac catheterization for clinical indications at Mayo Clinic Rochester. PAH-ILD patients referred for catheterization >18 years who can exercise will be enrolled. PAH will be confirmed by standard criteria. We will screen 35 patients to reach target accrual of 24 total subjects. A separate control group of 6 participants was initially planned to be enrolled from the community for comparative analyses to the PAH-ILD group. As

of protocol v5 dated 05Jan2024, only 1 control patient was enrolled and recruitment of control subjects has been halted due to shifting study priorities of the PI for the healthy control population with other separate ongoing studies for healthy controls. Remaining 5 previously planned subjects will now be enrolled as PAH-ILD subjects to allow further study of treprostinil in the patient population of interest.

Exercise Catheterization procedure

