Muscle biopsies of the quadriceps muscle (on the same side as the leg blood flow assessment) will be performed at a separate visit at least 3 days remote from the maximal exercise test, using a modified Bergstrom needle as has been extensively utilized by [name] group, to directly assess the skeletal muscle mitochondrial oxidative capacity component of peripheral O_2 utilization.²⁶⁻²⁸ High-resolution respirometry will be performed on mitochondria freshly isolated from the biopsy sample. Approximately 100 mg of tissue will be homogenized, and mitochondria separated using differential centrifugation. Mitochondria are added to a 2 ml chamber (Oxygraph-2K, Orobos) and allowed to equilibrate. Glutamate (10 mM) and malate (2 mM) are added to stimulate State 2 respiration specific to Complex I, then ADP is added at saturating concentrations (2.5 mM) to induce State 3 respiration of Complex I. Cytochrome-c is added to verify mitochondrial membrane integrity. Succinate (10 mM) is added to stimulate State 3 respiration through Complex I+II and then rotenone (0.5 μ M) is added to inhibit complex I for State 3 respiration specific to Complex II. State 4 respiration (Leak) is induced by addition of oligomycin (2 μ g/ μ l) then the proton gradient is dissipated by sequential titration of 0.05 mM carbonylcyanide-4-(trifluoromethoxy)-phenylhydrazone to induce uncoupled respiration. Protein content of isolated mitochondrial is determined using a commercially available kit (DC Protein Assay, Bio-Rad). Mitochondrial respiration measures will be normalized to tissue wet weight (reflective of mitochondrial content) and mitochondrial protein (reflective of mitochondrial protein quality). *Maximum mitochondrial respiration* for the respiratory complexes (Complex I+II) will be reported in pmol O_2 /ml/sec (per tissue content) and in pmol O_2 / μ g mito/sec (per mitochondrial protein content). *Mitochondrial efficiency* will be calculated as Respiratory Control Ratio (State 3/State 4).^{28,29}

Isolated quadriceps muscle mitochondria will be treated with glutamate and malate, and H_2O_2 emission (ROS) will be measured using Amplex Red oxidation (p mol/s/ μ g protein).³⁰

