Mitochondrial ATP production rate will be measured using a Fluorolog 3 (Horiba Jobin Yvon) spectrofluorometer. 10 μ l of isolated mitochondria suspension is added to 2 ml of buffer Z and 2.5 mM D-Glucose. *ATP production* (p mol/s/ μ g protein) is measured using an enzymatic system containing hexokinase and glucose-6-phosphate dehydrogenase to convert ATP to NADPH.^{21,23}

Expected Outcomes and Interpretation: We anticipate impaired Q_c reserve (<80% predicted based on expected $\Delta Q_c / \Delta VO_2 > 6$)³¹ in PAH-ILD during exercise on average. This will be associated with lactic acidosis and abnormal VE/ VCO_2 ratios. Following inhaled treprostinil therapy, there will be an acute improvement in exertional Q_c , lactate levels and VE/ VCO_2 ratios. Patients with values of skeletal muscle Dm and mitochondrial indices >median will have less peripheral impairment and a greater improvement in exercise Q_c with inhaled treprostinil.

Hypothesis #2 Baseline hemodynamic improvement in exertional cardiac output with inhaled treprostinil will predict subsequent NYHA class improvement at 3 months with chronic inhaled treprostinil therapy.

Research Design for Aim #2: Following Aim #1 patients with confirmed PAH will be initiated on outpatient inhaled treprostinil therapy with gradual uptitration to target dose as per standard clinical practice. Patients are typically re-evaluated within 3 months in our clinical practice with repeat comprehensive assessment including 6 minute walk distance, echocardiogram, NTproBNP and clinical assessment. Patient improvement will be documented by the patient and practicing providers by NYHA class (provider) and self-reported improvement (yes/no by the patient). More objective quantification of quality of life will be performed by the PAH-SYMPACT score and SF-36 scores. For patients who do not return for follow up assessment within the study time frame of 3 months, they will be remotely contacted with assessment of NYHA class, patient reported improvement and quality of life provided remotely.

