Expected Outcomes and Interpretation: We anticipate that the change in CO during exercise following inhaled treprostinil will predict NYHA class improvement with chronic inhaled treprostinil therapy by logistic regression. Exploratory analyses of baseline central and peripheral hemodynamic response to treprostinil stratified by improvement vs no improvement in NYHA class will also be performed. Changes in quality of life will be correlated with acute hemodynamic exercise response. Analyses will also be performed stratified by median skeletal muscle exercise Dm and mitochondrial oxidative capacity to determine the relationship of peripheral abnormalities with symptom response to chronic treprostinil.

Statistical analysis and power considerations: Sample size estimates were performed based on feasibility of recruitment within 1 year, and based on our current lab volumes and interest in PAH-ILD in our practice we anticipate being able to recruit 1 patient a month for a total of 23 patients with follow up clinical evaluations completed 3 months after last patient has been recruited. Prior exercise catheterization studies have shown improvements in PVR and PA pressure/CO slope ratios with acute vasodilator testing with as few as 10 patients.³³ Accordingly with 22 patients with paired measures, we anticipate having adequate power to assess for a within patient increase in exertional CO with inhaled treprostinil therapy by paired T test, and also to explore paired changes in the other novel indices in exertional ventilatory, peripheral and skeletal muscle O₂ transfer.

H. Drug supply

Inhaled treprostinil for acute vasodilator testing in our hemodynamic exercise catheterization laboratory will be provided at no cost by United pharmaceuticals for the 22 patients. Patients will then be prescribed chronic inhaled treprostinil therapy for chronic use as per clinical practice which will be billed and supplied clinically.

I. Anticipated results and potential pitfalls

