As described above we anticipate that patients with PAH-ILD will have impaired Q_c reserve with activity (exercise-rest Q_c <80% predicted based on normal measured change in VO₂ - the normal increase in Q_c being 6 ml/min per 1 ml/min in VO₂)³¹ during exercise at 20 watts for 5 minutes, which will improve following inhaled treprostinil. The degree of Q_c improvement during exertion with inhaled treprostinil will likely predict an improvement in NYHA class with 3 months of inhaled treprostinil as chronic therapy. Exploratory analyses of changes in other exertional pulmonary, central and peripheral indices with symptom improvement will also be performed.

J. Description of potential challenges and possible approaches to address them

Some patients with PAH-ILD may be O₂ dependent which precludes a face mask to directly measure gas exchange and VO₂ at the mouth. In these patients we will measure Q_c using the thermodilution method during rest and exercise which is the most accurate method in patients on supplemental O₂ therapy.³⁴ Another potential problem is failure to enroll the target number of participants for the study. This is an unlikely problem because the Mayo Clinic Pulmonary Hypertension program follows more than 300 adult PAH patients who are evaluated in the outpatient clinic annually. For the approximately 50 PAH patients a year who are newly initiating or intensifying therapy, cardiac catheterization is the standard of care, and ILD-PAH is one of the fastest growing areas in our clinical practice with our large ILD practice. In our laboratory, exercise RHC is routinely used in the evaluation of PAH and will provide no additional cost to this proposal. I also practice primarily in the PH clinic and cardiac catheterization hemodynamic lab which will maximize patient recruitment and feasibility. Importantly we have a successful track record of recruiting more than 15 patients a year for acute hemodynamic exercise studies in four completed^{14,15,35,36} and three ongoing studies of patients with pulmonary hypertension during exercise which do not overlap with this proposal. We will additionally provide remuneration to patients for their travel expenses and time to participate. Additional challenges relate to the acute effects of exercise on mitochondrial respiration that may confound the biopsy results. To mitigate this, the biopsy will be performed at

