least 3 days after the initial exercise study. All baseline hemodynamic and peripheral data will be interpreted and analyzed blinded to subsequent symptom response

Inclusion Criteria for PAH

- PAH due to Interstitial Lung disease being considered for inhaled treprostinil
- Resting right heart catheterization with mean pulmonary artery pressure>20 mmHg and PVR> 3 Wood units
- >=18 years of age

Exclusion criteria

- Inability to exercise
- Females who are pregnant

Inclusion Criteria for controls

- >=18 years of age
- No known heart failure, pulmonary hypertension, lung disease or muscular disease
- Ability to exercise
- No bleeding abnormalities

Schedule of assessments:

For PAH ILD patients

Visit 1

- Baseline assessments of PAH SYMPACT and SF-36 for quality of life will be performed
- Patients will undergo clinically indicated right heart catheterization with exercise as per clinical practice with internal jugular approach and right radial arterial line. Exercise will be performed up to 20 watts for 5 minutes.
- After exercising to 20 watts for 5 minutes, patients will be administered 32 mcg of inhaled treprostinil followed by 30 minutes of rest in the catheterization laboratory
- Repeat exercise up to 20 watts for 5 minutes will be performed after 30 minutes of rest.
- Simultaneous echocardiogram will be performed at rest and exercise.
- 10 ml of blood at rest and 5 ml with exercise will be stored at rest and exercise from the baseline phase. In addition high sensitivity troponin levels will be measured at rest and exercise before and after inhaled treprostinil.
- Following the second exercise phase Visit 1 will be completed

Visit 2 (optional muscle biopsy)

- Patients will be offered an optional muscle biopsy component with percutaneous needle biopsy in [name] laboratory for skeletal muscle mitochondrial assessment. Remuneration of \$200 will be provided for completion of the muscle biopsy component

Virtual Visit 3 (end point assessment)

- Patients will be contacted remotely at 4 months to mail back repeat PAH SYMPACT and SF-36 questionnaires for end point assessment of quality of life. Patients will be contacted by phone to assess NYHA class by Principal Investigator.

PAH-ILD subjects

Study Activity	Visit 1 Day 0	Visit 2 Day 3-14 (+/-)	Virtual Visit 3 Month 4 (+/- 14 days)
Informed Consent ¹	X		
Right Heart Catheterization	X		
Treprostinil Test dose	X		

Echocardiogram ²	X		
Troponin ³	X		
Research blood ⁴	X		
Questionnaires ⁵	X		X

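### Relate exercise Dm and mitochondrial oxidative capacity to symptom response on their measured scale, not by halves cut at the sample median

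*Combined protocol and SAP*

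**What the plan says.** The point arises in section G (Study design), Hypothesis #2, Expected Outcomes and Interpretation. After the logistic regression of NYHA improvement on change in cardiac output (CO), and an analysis of quality-of-life change, the protocol adds: "Analyses will also be performed stratified by median skeletal muscle exercise Dm and mitochondrial oxidative capacity to determine the relationship of peripheral abnormalities". The other side of that relationship is how symptoms respond to long-term therapy. No model or test is named.

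Other passages that bear on it:

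- The same paragraph plans "Exploratory analyses of baseline central and peripheral hemodynamic response to treprostinil stratified by improvement vs no improvement in NYHA class". This concerns the acute response to the drug, grouped by outcome.
- Section I (Anticipated results and potential pitfalls) plans "Exploratory analyses of changes in other exertional pulmonary, central and peripheral indices with symptom improvement will also be performed". This concerns changes.
- Hypothesis #1, Expected Outcomes, uses the same cut when stating an expectation: "Patients with values of skeletal muscle Dm and mitochondrial indices >median will have less peripheral impairment and a greater improvement in exercise Q_c". It is a prediction, not an analysis rule.
- Mitochondrial assessments shows that the mitochondrial measure is continuous and is reported in two ways: "Mitochondrial respiration measures will be normalized to tissue wet weight (reflective of mitochondrial content) and mitochondrial protein".
- The Visit 2 schedule makes the biopsy voluntary: "Patients will be offered an optional muscle biopsy component".
- Patient numbers differ by place. Statistical analysis and power considerations gives 23 recruited and 22 with paired measures, while the research design for Hypothesis #1 says "We will screen 35 patients to reach target accrual of 24 total subjects".

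**The concern.** The stated purpose is to determine a relationship. Replacing a measured value by above or below the median treats a patient just over the cut like the highest in the sample, and unlike a near neighbour just under it. The cut also depends on who happened to be enrolled. In a sample of 22 to 24 that loss is not trivial, and for the mitochondrial measure the number may be lower still because the biopsy is optional.

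The analyses of acute response and of changes do not fill the gap, because they do not use these levels. The biopsy is a single sample taken at a separate visit, so it has no acute change to analyse: the level is all the information that it gives. What is at stake is the use made of data from an invasive procedure that the protocol lists among its innovations. The main results are not at stake.

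**Working it through.** The documents give no figure for this analysis, so there is none to reproduce. The sample-size paragraph concerns the paired t test on CO.

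**Inputs.** From the documents: n = 22 (also 23 and 24), optional biopsy, cut at the median. Assumed, because the documents are silent: correlations of 0.3 and 0.5, improvement rates of 50% and 30%, and n = 12 with a biopsy.

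**Information kept by the split.** With a linear relation, the efficiency of comparing halves relative to using the measure X is the squared correlation of X with the indicator of X above its median: Cov² / (Var X × 1/4).

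- Normal: Cov = φ(0) = 0.399, so 0.159 / 0.25 = 2/π = 0.637. Loss 36%.
- Uniform on (0, 1): Cov = 0.375 − 0.25 = 0.125, so 0.0156 / (1/12 × 1/4) = 0.750. Loss 25%.
- Lognormal, log-SD s = 0.5: 4(Φ(s) − 0.5)² / (exp(s²) − 1) = 0.1466 / 0.2840 = 0.516. Loss 48%.

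For a normal measure, 22 × 0.637 = 14.0 and 24 × 0.637 = 15.3 effective patients. Simulation with the sample median at n = 12 to 24 gives losses of 35.8% to 36.3%. For a binary outcome linear in the log odds, the loss is 35%, 33% and 27% at odds ratios of 1.5, 2 and 3 per SD.

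**Power, continuous outcome** (40,000 replicates, two-sided 5%, normal measure; type I error 0.049 to 0.052 for all three methods):

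| n | r | Pearson, measured | t test, halves | Spearman |
|---|---|---|---|---|
| 12 | 0.3 | 15.4% | 11.0% | 14.0% |
| 12 | 0.5 | 40.1% | 24.6% | 34.3% |
| 22 | 0.3 | 27.6% | 18.6% | 24.6% |
| 22 | 0.5 | 68.8% | 46.2% | 62.1% |
| 24 | 0.3 | 30.0% | 20.0% | 26.7% |
| 24 | 0.5 | 73.1% | 50.4% | 66.6% |

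Other shapes at n = 22, r = 0.5, in the same order: lognormal 64.5%, 38.0%, 52.4%; uniform 70.1%, 53.4%, 65.5%; true step exactly at the median 48.2%, 53.6%, 52.5%.

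**Power, NYHA improvement** (outcome cut from a latent normal variable with correlation r to the measure):

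| n | Improving | r | Exact rank-sum, measured | N−1 chi-square, halves |
|---|---|---|---|---|
| 12 | 50% | 0.5 | 22.8% | 16.0% |
| 22 | 50% | 0.3 | 16.6% | 14.6% |
| 22 | 50% | 0.5 | 42.9% | 34.1% |
| 22 | 30% | 0.3 | 15.6% | 11.5% |
| 22 | 30% | 0.5 | 39.2% | 27.5% |
| 24 | 50% | 0.3 | 19.0% | 17.8% |
| 24 | 50% | 0.5 | 47.8% | 39.9% |

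Type I error at n = 22 with half improving is 0.045 for the rank-sum and 0.052 for the chi-square. Fisher's test was not used as the comparator because its type I error there is 0.018, which would have flattered the measured-value analysis.

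**Second reading: the CO–NYHA regression refitted inside each half of 11.** At latent r = 0.5, an unpenalised one-predictor logistic fit has no finite estimate (separation, or one outcome only) in 5.3% of halves if half improve and 10.9% if 30% improve. In all 22 patients the figures are 0.1% and 0.5%.

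**The case against.** The strongest objection is about meaning. Stratified may mean that the preceding analyses are repeated within each half, as an exploratory look at effect modification. The 36% does not apply then. This stands as a limit on the figure. The purpose clause, which speaks of the relationship between peripheral abnormalities and symptom response, points to comparing the halves, but no test is named and the wording does not settle it. Refitting in halves of 11 brings its own difficulty, shown above.

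Second, continuous peripheral data are already set against symptom response elsewhere in the plan, and the median analysis is described as additional. That is true of acute responses and changes. It is not true of the level of Dm or of mitochondrial capacity.

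Third, the gain is small for NYHA class, the outcome that Hypothesis #2 names, and power is low either way with 12 biopsies. A true step at the median would reverse the order. All of this is right. The clear gain is for quality of life.

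Fourth, Dm may be missing too. Section J says that direct VO₂ measurement is not possible in oxygen-dependent patients, and section F's simplified Dm uses VO₂. The schedule lists the femoral catheter and leg blood flow only for controls, and section F attributes substantial error to Dm calculated without them. This may limit the Dm analysis more than the cut does. It is a reason to report the number with each measure, not a reason to keep the cut.

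**Conclusion.** The point holds, as a cheap improvement and not as a threat to the main results. The only stated analysis of the level of Dm or mitochondrial capacity against symptom response cuts both at the sample median. Read as a comparison of halves, it loses 36% of the information for a normal measure and linear relation, and 25% to 48% across the uniform and moderately skewed shapes examined.

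At n = 22 the cost in power is about 23 points (69% v 46%) for a continuous outcome at r = 0.5 and 9 points (28% v 19%) at r = 0.3. For NYHA improvement it is 9 to 12 points at r = 0.5 and 2 to 4 points at r = 0.3. These rest on assumed correlations and improvement rates. The analysis is exploratory, and the paired t test on CO and the CO–NYHA logistic regression are untouched.

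**What to change.** Replace the median sentence under Hypothesis #2, Expected Outcomes, with wording to this effect:

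> Exercise Dm and mitochondrial oxidative capacity (Complex I+II maximum respiration, on one normalisation named in advance) will each be related, as measured, to NYHA improvement in a single-predictor analysis, and to quality-of-life change by correlation with a 95% confidence interval. The number of patients with each measure will be reported. Median groups will be used for display only.

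For NYHA improvement, name either the rank-sum test or penalised logistic regression in advance. If the Hypothesis #1 expectation about improvement in exercise cardiac output is tested, use measured values there too. If repetition within halves was intended, say so.

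The cost is one or two sentences and no new data. The downside is that the correlation assumes a roughly linear relation. A scatter plot and a Spearman sensitivity analysis cover that (62% power against 69% at n = 22, r = 0.5). If the truth were a step exactly at the median, the halves would do slightly better (54% against 48%).

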Muscle Biopsy ⁶		X	

¹Informed consent will be obtained before research activities are conducted

²Echocardiogram at rest and during exercise during RHC

³Troponin to be drawn at rest and exercise before inhaled treprostinil during RHC

⁴10 ml of blood at rest and 5 ml with exercise will be stored at rest and exercise from the baseline phase

⁵PAH SYMPACT and SF-36 questionnaires will be mailed. Phone call by PI to assess NYHA class.

⁶optional

For healthy controls

Visit 1

- Healthy controls will be recruited by advertisement and will undergo right heart catheterization with exercise with internal jugular approach and right radial arterial line as per standard clinical practice. Exercise will be performed up to 20 watts for 5 minutes, followed by 3 minute stages to peak exhaustion.
- A 5 french femoral venous flush catheter will be placed through which cold saline will be infused with sampling of temperature using a very small .025" Physitemp temperature wire (https://physitemp.com/flexible-implantable-probes_p101) placed parallel in the femoral vein through an additional venous puncture. This will allow direct measurement of leg blood flow during rest and exercise, and also allow femoral venous blood gas sampling during rest and exercise.
- Simultaneous echocardiogram will be performed at rest and exercise. Coronary sinus blood gases will also be collected at rest and during 20 watts of exercise through right heart catheterization.
- 10 ml of blood at rest and 5 ml with exercise will be stored at rest and exercise from the baseline phase. In addition, high sensitivity troponin levels will be measured at rest, 20 watts and peak exercise
- Following exercise to complete exhaustion, and a rest period of 30 minutes, healthy controls will then undergo knee extensor exercise to exhaustion with ankle weights attached in the seated position in the catheterization laboratory to isolate quadriceps muscle function with measurement of leg blood flow, blood gas sampling and central hemodynamics. Following this, the catheterization procedure will be complete.
- Remuneration of up to \$200 will be provided for Visit 1
- Screening for pregnancy will be performed prior to catheterization as per standard clinical practice.

Visit 2 (optional muscle biopsy)

- Patients will be offered an optional muscle biopsy component with percutaneous needle biopsy in [name] laboratory for skeletal muscle mitochondrial assessment

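### Nothing blinds the PI, who rates follow-up NYHA class by phone, to the acute cardiac-output response meant to predict it, and the rater, mode and time of that rating are inconsistent

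*Combined protocol and SAP*

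**What the plan says.** The Hypothesis 2 analysis is a logistic regression of NYHA improvement on the acute change in exercise CO after inhaled treprostinil (section G, expected outcomes for Aim 2).

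**Who rates, and how.**
- Schedule of assessments, Virtual Visit 3: "Patients will be contacted by phone to assess NYHA class by Principal Investigator". Footnote 5 of the PAH-ILD schedule table agrees: "Phone call by PI to assess NYHA class".
- Research Design for Aim #2 assigns the rating to practising providers and adds a separate patient report: "NYHA class (provider) and self-reported improvement (yes/no by the patient". Review is in clinic, and the phone is a fallback: "For patients who do not return for follow up assessment within the study time frame of 3 months, they will be remotely contacted".

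**When.**
- Hypothesis 2 and section I refer to 3 months of chronic therapy.
- The statistics section has "follow up clinical evaluations completed 3 months after last patient has been recruited".
- The schedule puts the assessment at month 4, plus or minus 14 days.

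**Blinding.** The only statement is at the end of section J: "All baseline hemodynamic and peripheral data will be interpreted and analyzed blinded to subsequent symptom response".

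**Baseline.** The Visit 1 text names only PAH-SYMPACT and SF-36. Footnote 5 attaches the PI's NYHA call to a questionnaire row ticked at both Visit 1 and Visit 3.

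**The concern.** NYHA class is a judgement, and here it is made by phone. If the person making it knows whether the patient's CO rose at Visit 1, expectation can enter the rating in exactly the direction Hypothesis 2 predicts. A positive regression would then mix true prediction with rater expectation, and nothing in the planned analysis could separate them. Once ratings have been made unblinded, this cannot be repaired at the analysis stage.

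The inconsistencies are a second problem. Improvement needs one baseline, one rater, one mode and one time. As written, two analysts could follow different sections and build different outcome variables from the same patients.

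**Working it through.** **1. Direction of the blinding.** The section J sentence keeps the predictor (haemodynamic reading) independent of the outcome (symptom response). The risk here runs the other way, from knowledge of the predictor to the rating of the outcome. No section addresses that direction, whether the rater is the PI or a treating provider.

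**2. Does the PI know the CO response?** This is not stated. Section J says, in the first person, "I also practice primarily in the PH clinic and cardiac catheterization hemodynamic lab", and in section F the same author plans to apply the invasive exercise methods personally. If that author is the PI, as the text suggests, knowledge is likely, but it remains an inference.

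**3. Sections compared.**

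| Item | Aim 2 design / statistics section | Schedule and footnote 5 |
|---|---|---|
| Rater | Practising provider | PI |
| Mode | Clinic; remote only for non-returners | Phone, unconditional |
| Time | 3 months | Month 4 ± 14 days |
| Baseline NYHA | Not described | Absent from Visit 1 text; implied by footnote 5 |

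**4. Timing (30.44 days per month).**
- Month 4 is 4 × 30.44 = 121.8 days, so the window is days 107.8 to 135.8.
- Three months is 3 × 30.44 = 91.3 days, which lies outside the window if both are counted from Day 0.
- If month 4 is meant as 3 months on drug, chronic therapy must start between 107.8 − 91.3 ≈ 16 and 135.8 − 91.3 ≈ 44 days after Day 0. No section states the clock start.

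**5. What rater knowledge could do.** The plan gives no figure for Hypothesis 2 to reproduce. It gives 22 patients with paired measures; everything else here is assumed.
- CO change x is drawn from N(0,1), with no true association with NYHA.
- The probability of being rated improved is p0 + d above the median of x and p0 − d below it.
- The test is logistic regression on continuous x, two-sided 5%, with 40,000 simulated trials per setting for p0 = 0.50 and 20,000 for p0 = 0.35.
- Spurious odds ratio, high versus low CO response: [(p0 + d)/(1 − p0 − d)] ÷ [(p0 − d)/(1 − p0 + d)]. For p0 = 0.50 and d = 0.10 this is (0.60/0.40) ÷ (0.40/0.60) = 2.25.

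| Shift d | False-positive rate, likelihood-ratio test (score test), p0 = 0.50 | Spurious OR, p0 = 0.50 | Likelihood-ratio test (score test), p0 = 0.35 |
|---|---|---|---|
| 0 | 6.5% (5.3%) | 1.0 | 6.5% (5.3%) |
| 5 points | 8.1% (6.8%) | 1.5 | 8.5% (7.1%) |
| 10 points | 14.1% (12.2%) | 2.25 | 14.9% (12.8%) |
| 15 points | 24.1% (21.5%) | 3.4 | 25.7% (22.7%) |
| 20 points | 37.6% (34.3%) | 5.4 | 40.5% (36.7%) |

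The rate of 6.5% at d = 0 is the small-sample excess of the likelihood-ratio test, not bias. Repeat runs with 20,000 or more trials per setting agreed to within about 0.6 percentage points.

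**The case against.** - **The rater conflict is soft.** The PI works in the PH clinic and may be one of the practising providers. This stands; the mode and time conflicts are firmer.
- **Knowledge of the CO response is inferred.** The section J remark about the catheterisation laboratory is made to support recruitment. Read literally, the blinding sentence also means that the haemodynamics are read before the call or by someone else. But reading them first does not stop the PI knowing the result when the call is made, and nothing assigns the reading elsewhere.
- **Month 4 may simply be 3 months on drug.** This is possible, but it depends on an unstated start of therapy and leaves the 3-month wording in the Aim 2 and statistics sections unreconciled.
- **Baseline NYHA may be covered by footnote 5.** That is a fair reading, but the Visit 1 text should say so.
- **Other measures are not rated by the PI.** The plan states "Changes in quality of life will be correlated with acute hemodynamic exercise response", and patients complete those questionnaires. They also report improvement as yes or no, although no analysis of that item is planned. These help, but Hypothesis 2 names NYHA. A blinded rater would not remove patients' own expectations either.
- **The shifts are hypothetical.** This is correct. The table shows what bias could do, not what is expected, and it assumes that all 22 patients have an outcome.

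**Conclusion.** The concern holds. It is certain that no section blinds the NYHA rater to the CO response and that the mode and nominal time of the rating differ between sections. The named rater differs too, though the two descriptions could refer to one person. That the PI actually knows each CO response is likely but inferred.

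The size of any bias cannot be obtained from the documents. Under the assumptions shown, a 5-point shift does little harm, while 10 points or more at least doubles the false-positive rate (6.5% to 14.1% by likelihood-ratio test, 5.3% to 12.2% by score test) and produces a spurious odds ratio of 2.25 or more.

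The damage is confined to Hypothesis 2. The paired CO comparison for Hypothesis 1 does not use NYHA. This should be fixed because it affects one of the two stated hypotheses and the remedy is cheap.

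**What to change.** Keep NYHA improvement as the Hypothesis 2 outcome and amend the following.

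1. Have a study-team member or co-investigator without access to the Visit 1 haemodynamics rate follow-up NYHA from a fixed script, and record the rating before it is linked to the catheterisation data.
2. Record baseline NYHA before the Visit 1 catheterisation and add it to the Visit 1 text and the schedule table.
3. State one rater, one mode and one assessment time, with its clock start (Day 0 or start of chronic therapy), identically in Hypothesis 2, the Aim 2 design, section I, the statistics section and the schedule.
4. Report the planned PAH-SYMPACT and SF-36 correlations beside the NYHA result, as the check not rated by the PI. Patient-reported improvement (yes/no) could be added if an analysis is specified for it.

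The cost is a small protocol amendment with no new patients, visits or procedures. The safety plan for depressive symptoms shows that a study team and a co-investigator exist; the sponsor must confirm that the chosen rater has no access to the haemodynamics. The PI gives up the rating. Any patients the PI has already rated should be flagged and examined in a sensitivity analysis.
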